#### 6.2 SOFTWARE

Analyses will be conducted using SAS Version 9.2 or higher.

## **6.3** CHANGES TO PLANNED ANALYSES

Draft versions of the SAP will be numbered sequentially as Version 0.0i. The final approved version will be numbered as Version 1.00. Revisions after the "Final" version will be numbered as Version 1.0x. The Clinical Study Report will document any changes made after the final version approved before the data base lock.

# 7.0 DESCRIPTION OF THE STUDY POPULATIONS

All tables, figures, and listings must include a population descriptor (e.g., ITT population, Safety Population, PKEVAL Population, or PK Population) in the title.

## 7.1 **DISPOSITION**

Subject disposition summaries will be presented by treatment arm and treatment sequence and will include the number of subjects randomized, the number and percentage of randomized subjects in the Safety, ITT, PKEVAL, and PK populations, as well as the number and percentage of subjects who complete the study. The summaries will also include the reasons for early discontinuation from the study.

#### **7.2** DEMOGRAPHIC AND BASELINE CHARACTERISTICS

A summary of demographics and baseline characteristics will be presented by treatment arm and treatment sequence for the ITT, Safety, Evaluable PK and PK populations. The demographic characteristics will consist of age, sex, ethnicity, and race using descriptive statistics.

Age will be calculated based on the following conditional algorithm:

- Has the subject had his/her birthday this year?
  - Yes, then AGE = (year of informed consent) (year of birth).
  - No, then AGE = (year of informed consent) (year of birth) 1.

Clinical baseline characteristics summaries will include BMI, Psychosocial History. Clinical baseline characteristics will summarized by treatment group, sequence, and overall.

## 7.3 MEDICAL HISTORY

Medical history will be coded using MedDRA dictionary. A medical history listing will be presented.

# **8.0** PRIOR AND CONCOMITANT MEDICATIONS

All medications recorded on the CRFs will be coded using the WHO DRUG Dictionary. Prior and concomitant medications will be summarized by treatment arm in the safety population by anatomical therapeutic chemical (ATC) Class Level 4 and WHO Drug base substance preferred name.

Prior medications are defined as medications with stop dates occurring before the date of first administration of any study treatment component. Concomitant medications are defined as medications with start dates occurring on or after the date of first administration of any study treatment and no more than 30 days after the last administration of study treatment. Medications with start and stop dates that bracket the date of first administration of any study treatment will be summarized as both prior and concomitant medications.

Medications that clearly stopped prior to date of first administration study treatment will be included in the prior medications table, and medications that clearly started on or after date of first administration of

study treatment will be included in the concomitant medications table. All other medications will be included in both the prior and concomitant medications tables.

Prior and Concomitant medication will be summarized for the safety population.

# 9.0 EFFICACY ANALYSES

The primary objective of the study is to assess PK profile. The efficacy evaluation is for exploratory purpose only.

## 9.1 NUMERICAL RATING SCALE (NRS) FOR PAIN

Numerical Rating Scale (NRS) for pain will be used to assess the worst daily and average daily pain. The NRS is an 11-point scale with anchors 0 (no pain) and 10 (worst pain imaginable). Subjects will record their Worst and Average Pain Score over the past 24 hours in an electronic diary on a daily basis.

The average of the worst daily pain (AWDP) at a visit will be defined as the average of the non-missing worst daily pain score since previous visit; the average of the average daily pain (AADP) at a visit will be defined as the average of the non-missing average daily pain score since previous visit.

Changes from baseline in AWDP will be defined as Baseline AWDP – Post-baseline AWDP. A positive change is indicative of improvement. Similarly, changes from baseline in AADP will be defined as Baseline AADP – Post-baseline AADP. A positive change is indicative of improvement.

Changes from baseline in AADP and in AADP will be summarized over post-baseline visits by treatment group based on the subjects who have provided baseline assessments.

AADP and in AADP will be summarized over post-baseline visits by treatment group.

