#### Efficacy Variables:

The following exploratory efficacy variables will be assessed during the study:

- Urine toxicology: Frequency and incidence of positive results for opioids (excluding BPN) and other nonopioid drugs.
- NRS scale for pain: change from baseline in weekly average of daily Worst Pain score.

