### 10.4.2 Numerical Rating Scale (NRS) for Pain

The NRS is an 11-point scale with anchors 0 (no pain) and 10 (worst pain imaginable). Subjects will record their Worst and Average Pain Score over the past 24 hours in an electronic diary on a daily basis. Study personnel and subjects will undergo training on how to complete the NRS assessment.

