#### 10.6.2 Numerical Rating Scale for Pain

The weekly average of daily Pain Intensity (PI) will be calculated based on non-missing NRS scores (i.e., the missing daily scores will not be used in the calculation for the average). This weekly average will be called PI for that week. Pain Intensity Difference (PID) for a post-baseline Week i will then be derived as

PID at week 1i = PI at baseline – PI at week i.

Based on this definition, a positive PID is indicative of an improvement. The efficacy endpoint will be the change from Baseline in the weekly average of the daily Worst Pain score.

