#### 12.3.4 Analysis of Efficacy

The frequency and incidence of urine toxicology results positive for opioids other than BPN, and positive results for other, non-opioid, drugs of abuse will be listed by subject and summarized by Group.

Change from Baseline in the weekly average of the daily Worst Pain score will be listed by subject and summarized by Group.

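### The SAP averages daily pain scores between visits and reports by visit, while the protocol's exploratory pain endpoint is a weekly mean; the change is undeclared and leaves the protocol endpoint untabulated

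*SAP*

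**What the plan says.** The protocol is consistent about the unit of analysis. Section 10.6.2 states: "The weekly average of daily Pain Intensity (PI) will be calculated based on non-missing NRS scores". It adds: "This weekly average will be called PI for that week". It then takes the difference between baseline and week i, and names the endpoint: "The efficacy endpoint will be the change from Baseline in the weekly average of the daily Worst Pain score". The synopsis lists the same variable, and section 12.3.4 plans its analysis: "Change from Baseline in the weekly average of the daily Worst Pain score will be listed by subject and summarized by Group". The data are daily (section 10.4.2): "Subjects will record their Worst and Average Pain Score over the past 24 hours in an electronic diary on a daily basis".

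SAP 9.1 keeps the daily diary but changes the window. AWDP, its worst-pain variable, is the "average of the non-missing worst daily pain score since previous visit", and AADP is built the same way for average pain. The reporting sentence reads: "Changes from baseline in AADP and in AADP will be summarized over post-baseline visits by treatment group". AADP appears twice there and again in the sentence that follows, so AWDP is defined but never listed for summary. No weekly pain mean appears anywhere in the SAP. SAP 6.3, on changes to planned analyses, covers version numbering only.

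**The concern.** This is a stated rule that produces a different quantity from the protocol endpoint, not a missing detail. Visit timing follows pharmacokinetic sampling: daily around the intensively sampled doses and through the first nine days of Group 3, weekly in much of the rest. A mean since the last visit can therefore be one diary entry at one visit and seven at the next, in a pattern that differs by Group. Two things are at stake: whether the weekly endpoint can be found in the report, and whether adjacent columns of the pain tables have comparable precision. Taken literally, the summary sentences also omit worst pain, which is the variable the protocol names.

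**Working it through.** **Step 1: check the visit days against the plan's own durations.** Protocol 9.1 gives up to 13, 22 and 17 weeks of treatment. From the last visit in Tables 1 to 3: (92 − 1)/7 = 13, (155 − 1)/7 = 22, (120 − 1)/7 = 17. All agree. For Group 3 I used Day 120 from Table 3. The protocol synopsis and SAP 4.3 place that visit on Day 127, which would give (127 − 1)/7 = 18 weeks; those places need reconciling.

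**Step 2: visit days read from the tables.**
- Group 1: 1, 2, 8, 15, 22–27, 29–34, 36–41, 43–48, 50; extension 57, 64, 71, 78, 85, 92.
- Group 2: 1, 2, 8, 15, 22, 29, 31, 36, 43, 50, 57, 59, 64, 71, 78, 85–90, 92, 95, 99, 106, 113; extension 120, 127, 134, 141, 148, 155.
- Group 3: 1–9, 15, 22, 29, 36, 38, 43, 50, 57, 64, 66, 71, 78, 85, 92–97, 99, 102, 106, 113, 120.

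**Step 3: window length = visit day minus previous visit day.**

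| | Windows | 1 day | 2–6 days | 7 days | Not 7 days |
|---|---|---|---|---|---|
| Group 1, treatment | 28 | 21 | 5 | 2 | 26 (93%) |
| Group 2, treatment | 25 | 6 | 8 | 11 | 14 (56%) |
| Group 3, treatment | 32 | 13 | 8 | 11 | 21 (66%) |
| Group 1 with extension | 34 | 21 | 5 | 8 | 26 (76%) |
| Group 2 with extension | 31 | 6 | 8 | 17 | 14 (45%) |

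Pooled, 26 + 14 + 21 = 61 windows are not weeks: 61 of 85 (72%) in the treatment phase and 61 of 97 (63%) with the extension. The protocol's rule would give 13, 22 and 17 windows, all of 7 days; the SAP's gives 34, 31 and 32.

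**Step 4: sensitivity to what counts as a visit.** Merge each run of consecutive-day visits into its first day. Every Group 1 window then becomes 7 days. In Group 2, 6 of 19 treatment windows are still not weeks (2, 5, 2, 5, 3 and 4 days). In Group 3 it is 7 of 19 (those six plus one of 14 days). The SAP states no merging rule.

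**Step 5: precision.** The documents give no SD or correlation for pain scores, so this is an assumption shown as a range. If any two days within a subject have correlation ρ, the SD of a one-day score divided by that of a 7-day mean is √[7/(1 + 6ρ)]:
- ρ = 0.3: √(7/2.8) = 1.58
- ρ = 0.5: √(7/4.0) = 1.32
- ρ = 0.7: √(7/5.2) = 1.16
- ρ = 0.9: √(7/6.4) = 1.05

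For within-subject error alone, with independent days, the ratio is √7, about 2.6. These ratios are for the visit score itself; those for change from baseline also depend on the baseline window, which is not settled.

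**The case against.** Several points on the other side stand. The efficacy evaluation is exploratory (SAP 9.0), the pain analysis is descriptive, and no sample size rests on it. Protocol 12.1 allows the SAP to make changes, so the fault is that this one is undeclared and unexplained, not that it is forbidden. Daily scores are collected, so weekly means remain derivable. SAP 9.1 does not define a visit, and Table 1 does not mark the days after each crossover injection as outpatient visits. However, Table 1 schedules the pain scale, vital signs and urine screens on those days, and merging does not make Groups 2 and 3 weekly.

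A reader might also infer three stronger things that the documents do not support:
- **That the visit rule hides waning at the end of the Group 1 dosing interval.** SAP 9.1 summarises each visit separately and pools nothing across visits. The window closing at the next pre-dose visit holds days 6 and 7 alone; a weekly mean would blend them with days 1 to 5.
- **That most windows are non-weekly in every Group throughout.** This holds for the treatment phase. With the extension, 17 of 31 Group 2 windows are weeks.
- **That variability is several times larger.** The 2.6-fold SD ratio needs independent days and ignores stable differences between subjects. The SD shown in a table includes those differences, so 1.05 to 1.58 is the fairer illustration.

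**Conclusion.** The point holds as an undeclared departure from the protocol's exploratory pain endpoint. The contradiction rests on the text alone. The window counts assume that each scheduled day is a visit; under the most favourable merging, about a third of the Group 2 and Group 3 treatment windows (6 of 19 and 7 of 19) still fail to be weeks. Precision is unequal across visits and Groups, modestly so if daily scores are strongly correlated. As SAP 9.1 stands, the protocol's weekly worst-pain change would not appear in the tables, and worst pain is not listed for summary at all. No pharmacokinetic conclusion, error rate or sample size is touched. It should be fixed because the correction is cheap, but it does not threaten the study's main results.

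**What to change.** Revise SAP 9.1 as follows:
- Define AWDP and AADP by 7-day study week counted from the first CAM2038 dose (Day 1 in Groups 1 and 2, Day 8 in Group 3), so that week i is dosing days 7(i − 1) + 1 to 7i. Average the non-missing days and report how many contributed.
- Report Group 3 Days 1 to 7, on sublingual buprenorphine, as a separate week so that those entries are not lost between baseline and Week 1.
- State a baseline window for pain that ends before the first study drug, for example the last 7 diary days. Say that it replaces the general rule in SAP 6.1 for this variable, because that rule is tied to randomization and Group 3 is not randomized. Present the week numbering and baseline window as SAP definitions; protocol 10.6.2 specifies neither.
- In both summary sentences, change the first AADP to AWDP.
- Label any by-visit summary as additional, and record the change and its reason.

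The cost is SAP wording and programming; no new data are needed. The revision should precede the lock of Groups 1 and 2, which SAP 9.3 places ahead of Group 3.

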## **9.2** URINE TOXICOLOGY

The urine toxicology for opioids other than BPN, and other non-opioid drugs of abuse will be measured via qualitative methods. Frequency and incidence of positive urine toxicology results will be summarized by treatment group.

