## 6.3 Exploratory Objectives

The exploratory objectives of the study are:

- To evaluate maintenance of treatment efficacy when transferring adult opioid-dependent subjects from SL BPN to CAM2038 q1w and q4w, as determined by urine toxicology.
- To evaluate subject-rated worst daily pain and average daily pain, using an 11-point numerical rating scale (NRS), following repeated SC administration of CAM2038 q1w and CAM2038 q4w in adult opioid-dependent subjects.

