### **10.4.1 Urine Toxicology**

A 12-panel UDS will test for the following drugs of abuse: THC/marijuana, cocaine, phencyclidine (PCP), morphine and its related metabolites derived from opium (opiates), methamphetamines, methadone, amphetamines, barbiturates, benzodiazepines, methylenedioxymethamphetamine (MDMA), oxycodone and propoxyphene.

Urine drug screen samples will be collected at the time points specified in Table 1 (Group 1), Table 2 (Group 2), and Table 3 (Group 3) using a urine collection cup containing a temperature sensor. Specimen authenticity will be verified at the site using this sensor to measure the urine temperature immediately following collection. The temperature of a urine sample within 4 minutes of voiding should fall within the range of 32.2 to 37.7 degrees Celsius (90 to 100 degrees Fahrenheit). If test results are outside these ranges, the subject will be asked to immediately provide another urine sample. If this second sample is outside of the temperature range, the sample will be counted as 'missing', and should not be sent for analysis (any such samples must be documented in the subject's records). Direct observation approach to obtaining urine samples may be used if the Investigator deems necessary.

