# 4.0 STUDY DESCRIPTION

## 4.1 STUDY OBJECTIVES

Primary objectives of the study are:

- To evaluate the steady state PK of buprenorphine (BPN) and norbuprenorphine (norBPN) following repeated subcutaneous (SC) administration of CAM2038 q1w (50 mg/mL) at 4 different injection sites in adult opioid-dependent subjects with chronic pain.
- To evaluate steady state PK of BPN and norBPN following repeated SC administration of CAM2038 q4w (356 mg/mL) with the buttock as the injection site in adult opioid-dependent subjects with chronic pain.

The secondary objective of the study is:

- To evaluate the safety and tolerability of CAM2038 q1w and CAM2038 q4w in adult opioid dependent subjects with chronic pain.
- To assess relative bioavailability of BPN at steady state following repeated SC administration of 160 mg CAM2038 q4w compared with repeated SL administration of 24 mg BPN in adult opioid-dependent subjects with chronic pain

The exploratory objectives of the study are:

- To evaluate maintenance of treatment efficacy when transferring adult opioid-dependent subjects from Sublingual (SL) BPN to CAM2038 q1w and q4w, as determined by urine toxicology.
- To evaluate subject-rated worst daily pain and average daily pain, using an 11-point numerical rating scale (NRS), following repeated SC administration of CAM2038 q1w and CAM2038 q4w in adult opioid-dependent subjects.

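### SAP 9.2 summarizes urine toxicology only by treatment group, so the planned analysis does not address maintenance of efficacy on transfer from SL BPN

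*SAP*

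**What the plan says.** Protocol 6.3 sets the exploratory objective: "To evaluate maintenance of treatment efficacy when transferring adult opioid-dependent subjects from SL BPN to CAM2038 q1w and q4w, as determined by urine toxicology". SAP 4.1 repeats it.

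For the analysis, SAP 9.2 has one sentence: "Frequency and incidence of positive urine toxicology results will be summarized by treatment group". Protocol 12.3.4 covers opioids other than BPN and adds that "positive results for other, non-opioid, drugs of abuse will be listed by subject and summarized by Group". Neither section names a visit, a period, a baseline for urine results, or a comparison across the transfer. SAP 9.0 calls the efficacy evaluation exploratory.

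On specimens outside the temperature range, Protocol 10.4.1 first requires an immediate second sample, then says: "If this second sample is outside of the temperature range, the sample will be counted as 'missing', and should not be sent for analysis". It also offers a safeguard: "Direct observation approach to obtaining urine samples may be used if the Investigator deems necessary". Protocol 12.3.5 deals with missing safety and PK data. Neither document says how a missing urine sample enters a rate.

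**The concern.** Maintenance on transfer is a question about change within a subject, so it needs a result before the switch and a result after it. A frequency and an incidence per treatment group contain no such contrast. SAP 4.2 uses the term treatment group for Groups 1 to 3. Read that way, Group 3's figure may cover both its week of supervised SL BPN and its CAM2038 period.

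The omission is specific to urine. SAP 9.1 defines a change from baseline for pain, SAP 11.3 summarizes COWS and SOWS over time, SAP 11.5 gives laboratory values by visit with shift tables, and SAP 11.8 gives ECG by visit. The general baseline in SAP 6.1 does not fill the gap: it is tied to the date of randomization, and Group 3 is not randomized.

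At stake is whether the reported figure can tell maintained abstinence from lost abstinence, and whether invalid specimens drop out of it unseen.

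**Working it through.** The documents give no rate, margin or power for urine toxicology, so there is no planned figure to reproduce. The check counts scheduled screens and then tests what a group rate can show.

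**1. Scheduled screens** (urine drug screen rows of Protocol Tables 1 to 3, one screen per listed day, Day 1 in Groups 1 and 2 and Day 8 in Group 3 taken as pre-dose)

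| Group | Before transfer | After transfer | Share before |
|---|---|---|---|
| 1 | Screening, D1 = 2 | 3 (D2, D8, D15) + 4 (D22, 29, 36, 43) + 20 (four runs of five days) + 1 (D50) + 2 (extension) = 30 | 2/32 = 6.3% |
| 2 | Screening, D1 = 2 | 25 to D113 + 2 (extension) = 27 | 2/29 = 6.9% |
| 3 | Screening, D1–D7, D8 = 9 | 25 | 9/34 = 26.5% |

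If the Group 3 Day 8 screen follows the injection, the share is 8/34 = 23.5%. Table 3 puts D1 to D6 in one column, and several other rows of that column are limited to Day 1 by footnote. The urine row has no such footnote, so daily screening is plausible but not stated. If one screen is meant, the total is 34 − 5 = 29, and 3 of 29 (10%) precede CAM2038, or 4 of 29 with Day 8.

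**2. What a pooled rate can show** (assumed rates; pooled = (a × before + b × after)/(a + b), with a and b the screen counts)

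- Group 3, a = 9, b = 25, pooled 15%, so 0.15 × 34 = 5.1. With 0% before, after = 5.1/25 = 20.4%. With 15% before, after = 15%. With 30% before, after = (5.1 − 2.7)/25 = 9.6%. Worsening, no change and improvement give the same figure.
- Group 3 with a = 3, b = 26, so 0.15 × 29 = 4.35. With 0% before, after = 4.35/26 = 16.7%. With 30% before, after = (4.35 − 0.9)/26 = 13.3%. The mixing is milder.
- Group 1, a rise from 0% to 20%: 30 × 0.20/32 = 18.8%. No change at 20% gives 20.0%. The rate is almost wholly post-transfer and has no reference value.

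**3. Uneven sampling.** In Group 1, 24 of the 28 post-transfer screens up to Day 50 (86%) fall on Days 22 to 48, and the six-week extension has 2. A sample-level frequency therefore follows the PK schedule. Any-positive rules have the same weakness. At a constant, independent 5% per sample (assumed), the chance of at least one positive is 1 − 0.95^n:

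- n = 1: 5%
- n = 2: 10%
- n = 6: 26%
- n = 28: 76%

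With no change at all, any-of-2 before against any-of-28 after would look like lost efficacy.

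**4. Twice-failed samples** (assumed rates; failures taken as leaving the denominator, which the documents do not state)

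- If a share p of samples would be positive and a share q of those is replaced by failing specimens, the reported rate is p(1 − q)/(1 − pq). With p = 20%, q = 50%: 0.10/0.90 = 11%. With p = 10%, q = 50%: 0.05/0.95 = 5%.
- The other direction is possible. With 10 positives per 100 and 10 failures that are all negative, the rate is 10/90 = 11%, above the true 10%.
- Bounds for a positive rate r among valid samples and a missing share m run from r(1 − m) to r(1 − m) + m. For r = 20%: 18% to 28% at m = 10%, and 16% to 36% at m = 20%. For r = 10%, m = 10%: 9% to 19%.

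**The case against.** The best defence is that the trial collects what is needed. Screens fall before and after transfer in every group, and Protocol 12.3.4 requires a by-subject listing. With about 56 subjects, a reader could trace individual changes. A reader might infer that the objective cannot be answered at all, or that only one rate per group will exist. Neither holds: the data are there, and the plan names both frequency and incidence, for opioids and for other drugs. The objective is also to evaluate maintenance; no test or margin is promised.

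Second, other opioid use is an exclusion criterion, so in Groups 1 and 2 the rate after transfer largely captures new positivity. That is fair, and it makes the mixing problem mainly one for Group 3. SAP 9.2 also does not say that pre-transfer samples are pooled. It does not say that they are excluded either.

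Third, a reader might infer that the missing-sample rule can only favour CAM2038. It cannot be put so strongly. Failures from non-users raise the rate, and failures before transfer would lower the reference. The temperature limit applies to urine read within 4 minutes of voiding, so a failure is not proof of a substituted specimen. Immediate re-collection and optional observation also reduce the problem.

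What remains is that a listing is not a summary, and the summary that is planned does not bear on the stated objective.

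**Conclusion.** The point stands as a gap in the analysis plan. Followed as written, SAP 9.2 yields no before-versus-after or by-visit result for urine toxicology, so the planned summary does not speak to maintenance on transfer. The mixing of treatments in Group 3 is conditional on all samples entering its rate. The pre-CAM2038 share is then about a quarter under daily screening on Days 1 to 6, and about a tenth under a single screen.

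The missing-sample issue is real but of unknown size and depends on who fails the check; the rates in the working are illustrations. Exploratory status limits the weight of the point and leaves the primary PK objectives untouched. It is still worth correcting before database lock, because a better summary can be made from samples already scheduled.

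**What to change.** In SAP 9.2:

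- Tabulate results positive for opioids other than BPN by scheduled visit, separately for the pre-transfer period (Screening and Day 1 pre-dose; in Group 3 up to the Day 8 injection) and the post-transfer period.
- Use summaries that do not grow with the number of samples: the proportion positive at each visit, and each subject's proportion of positive samples per period. Avoid scoring a week as positive on any positive sample.
- Report how many subjects with no pre-transfer positive become positive after transfer. State the number of samples behind each period, and note that Groups 1 and 2 have only two pre-transfer samples. By the arithmetic above, this count must be read beside the by-visit proportions.
- State whether Group 3 is screened daily on Days 1 to 6.
- Report the number of twice-failed and missed samples, and say whether visits after early discontinuation count as missed. Repeat the by-visit table with these samples counted as not negative, beside the observed rate.

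No new visits or samples are needed. The cost is a few extra tables and a data field for failed samples, which Protocol 10.4.1 already requires sites to document. The sponsor also accepts a sensitivity figure that will be less favourable than the observed rate.
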